The ancillary study runs parallel with the larger ROSSEY RCT. Recruitment, enrollment, and baseline assessment are expected to last two months (September-November 2022). Enrolled participants will not receive the comic book and parent video series until after completion of the ROSSEY RCT Post 1 follow-up Survey to not bias the data of older siblings participating in the ROSSEY RCT. A follow-up assessment for Early Learning participants is anticipated to take place 10 months after the launch of recruitment (July-August 2023)

II. Aim 1

Evaluate if risk communication health education can increase uptake of COVID-19 mitigation measures, improve children's school attendance, and increase families' physical and mental well-being using a single-arm pre/post study.

III. Study Population

We will collaborate with the Yakima School District to recruit Early Learning students (3, 4 and 5 years old) and their parent or Guardian(s) into the research study. We will recruit Early Learning students into the study regardless of their participation in SARS-CoV-2 testing provided by the Yakima School District. This will allow us to evaluate the effect of the risk communication strategies on the uptake of SARS-CoV-2 testing and other mitigation measures.

IV. Sample Size

Early Learning is an ancillary study with no defined sample size. We will enroll and recruit participants for a total of eight weeks.

V. Enrollment Criteria

Parent/Guardian eligibility criteria for participation in the study include:

- Must have a child attending the Early Learning Program in the Yakima School District
- Must be able to provide informed consent and legal guardian assent either virtually, on the telephone, or in-person.
- Must have a permanent mailing address available for study staff to mail necessary materials OR a working email address.

VI. Study Procedures

Recruitment, Screening and Consent

Enrollment and recruitment of the Early Learning ancillary study will start the second academic year of the RCT (2022-2023). Study information in the form of a flyer will be sent home with students to parents through school email by the principal and posted on the school Parent Square site in September of 2022. In addition, ROSSEY staff will attend the Early Learning Open House to hand out study information and obtain the phone number or email address of interested parents. ROSSEY staff will follow up with interested parents and provide further information about the study.

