Families will have two options to enroll children in the study: online through a website portal (Project REDCap), or with assistance from study staff over the phone.

- Parents/guardians who choose to enroll children in the study online will provide informed consent by reading and e-signing consent and assent forms through a web-based REDCap portal, and then the participant's parent/legal guardian will complete a baseline survey (same enrollment and secondary outcomes survey from the RCT of the main study).
- Parents/guardians who choose to enroll with staff assistance over the phone will be verbally guided through the REDCap consent/assent forms, enrollment questionnaire and secondary outcomes questionnaire.

[figure not shown]
Parents who choose online enrollment will be screened for eligibility via the REDCap web-based portal. Parents who choose enrollment with staff assistance will be screened over the telephone. The online consent portal will encourage parents/legal guardians to contact research staff by phone or email to review the risks and benefits of study participation, or to review the study procedures outlined in the consent form. Since all children are under the age of 7, the parent or legal guardian will sign the consent form, and the child will provide verbal assent if able. Electronic copies of the e-signed consent and assent documents will be automatically emailed to participants. For those who enrolled by telephone, copies of the consent and assent documents will be sent to the participants either via e-mail, through the mail, or in person.

NEEDS A SECTION ON BASELINE SURVEY.

After enrollment is complete, parents/guardians of study participants will take part in the following study procedures:

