Risk Communication: Risk communication, in the form of comic books with accompanying read-along videos for the children (n=3) and videos for the parents (n=2) will be distributed in English and Spanish to all enrolled students within two weeks of completion of the ROSSEY RCT final assessment (December 2023). Three comic books will be distributed by mail and parents will be sent a password-protected link with the mailed comic to access the parent videos and comic book read-along videos. All intervention materials (i.e., children's comic books and parent videos) will be distributed after the final assessment of the larger ROSSEY RCT study is complete. The delay is to eliminate possible contamination of the RCT by siblings of comparison students who will receive the comic books as part of this ancillary study.

Outline of Early Learning Study Procedures

Follow-up Survey: We will contact parents 6 weeks after the risk communication intervention distribution. Parents will be asked to complete the follow-up survey either online or by phone. The surveys will ask for updates to their contact and demographic information, child's COVID-19 vaccination status, and child's SARS-CoV-2 mitigation behaviors and the secondary outcome measures.

Following the protocol from the ROSSEY RCT, the post assessment will take place over 6 weeks, allowing two weeks for final contact prior to closure. For EL participants with missing or phone numbers no longer in service, ROSSEY staff will contact the YSD to 1) determine if the student is still attending YSD, 2) find out school and teachers name to send a notice through the school to the parent letting them know we are trying to reach them. Students determined to still be enrolled at YSD, and are non-responders to the follow up survey, will receive an at home visit by ROSSEY staff as a final attempt to reach student and parent to complete survey. Follow-up assessment closure will take place one week after completion of home visits.

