ReOpening Schools Safely and Educating Youth (ROSSEY Study) – Early Learning Ancillary Study

Clinical Trials.gov : NCT05965323

June 30, 2022

STATISTICAL ANALYSIS PLAN

1. Introduction to the SAP

This statistical analysis plan (SAP) describes the plans for statistical analyses that will address the study's protocol objectives.

2. Study Schema and objectives

Purpose:	Evaluate if risk communication health education can increase uptake of COVID-19 mitigation measures, improve children's school attendance, and increase families' physical and mental well-being using a single-arm pre/post study.
Design:	A single-arm pre/post-study
Central Hypotheses:	Our central hypotheses are that students and parents who view the risk communications will be more likely to have increased COVID-19 testing and vaccine uptake.
Primary Objectives:	
• To determine if implementing three COVID-19 education comic books for children and two COVID-19 education videos for parents will increase COVID-19 testing and vaccine uptake in children.
Secondary Objectives:	
• To determine if implementing three COVID-19 education comics books for children and two COVID-19 education videos for parents will increase physical activity, improve sleep, increase emotional regulation in children.• To determine if implementing three COVID-19 education comics books for children and two COVID-19 education videos for parents will increase physical activity, improve sleep, decrease depression and anxiety in parents
Population:	Children ages 3-5 enrolled in the Early Learning program in Yakima School District
Study Size:	Early Learning is an ancillary study with no defined sample size. We will enroll and recruit participants for a total of eight weeks
Primary Outcome Measurements:	
A. COVID-19 testing data available through self-reported surveyB. COVID-19 vaccine data available through self-reported survey
Study Duration:	11 months – September 2022- August 2023

3. Study Design

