The ancillary study runs parallel with the larger ROSSEY RCT. Recruitment, enrollment, and baseline assessment are expected to last two months (September-November 2022). Enrolled participants will not receive the comic book and parent video series until after completion of the ROSSEY RCT Post 1 follow-up Survey to not bias the data of older siblings participating in the ROSSEY RCT. A follow-up assessment for Early Learning participants is anticipated to take place 10 months after the launch of recruitment (July-August 2023)

4. Sample size and power

Early Learning is an ancillary study of 50 participants. We will enroll and recruit participants for a total of eight weeks.

Enrollment Criteria

Parent/Guardian eligibility criteria for participation in the study include:

- Must have a child attending the Early Learning Program in the Yakima School District
- Must be able to provide informed consent and legal guardian assent either virtually, on the telephone, or in-person.
- Must have a permanent mailing address available for study staff to mail necessary materials OR a working email address.

5. Population and Data Source

Participants enrolled in the ROSSEY Study: 50 children and parents from the Yakima School District. Any participants subsequently found to be ineligible will be removed. The data sources for the primary analyses are COVID testing results received from the school administration and the survey data as entered in REDCap. The COVID vaccination status data is obtained through the parent and child surveys, completed in REDCap.

6. Presentation of analyses

For each of the continuous outcomes (including the primary outcome), the mean and standard deviation will be presented pre/post intervention and p value. For binary outcomes, the percentage and frequency of children in the outcome category of interest (e.g., percentage vaccinated) will be presented pre/post and p value.

7. Outcome Definitions

a. Primary Outcomes

The two co-primary outcomes of the trial are COVID-19 testing and COVID-19 vaccine uptake. COVID-19 data are captured through school testing and self-reported survey, and COVID-19 vaccine uptake data are captured through self-reported survey. All children and parent data will be included in the intention-to-treat analysis.

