COVID-19 testing: Health reports from the school are provided for the 2022-2023 school year that list positive covid test results of study participants with the date of testing and the school of attendance. Positive test results for COVID will be a binary, yes/no variable.

COVID-19 vaccine uptake: Parents are asked at enrollment to report their vaccination status and their child's vaccination status. At post survey, the parent is asked to report if they or their child have received any COVID-19 vaccine or booster since enrollment. Vaccination status will be a binary, yes/no variable.

b. Secondary Outcomes

Secondary outcomes for the trial include the following outcomes from the PROMIS – Pediatric and Parent Proxy Instruments. The PROMIS instruments used are Children's physical activity (PA), sleep, stress, depression, and anxiety. Parents' PA, sleep, stress, depression and anxiety. The final score is represented by the T-score, a standardized score with a mean of 50 and a standard deviation (SD) of 10.

The outcome measures will be collected at pre-and post-assessment.

8. Primary exposure definition

Receiving the educational materials: three comic books and two graphic motion videos.

9. Interim analysis plan

For this study, there was no interim analysis.

10. Multiple testing

We will adjust for multiple testing by controlling FDR.

11. Missing Data

We will inspect missing data mechanisms and the amount of missing data. We will conduct an additional sensitivity analysis with multiple imputations using multivariate imputation with chained equations (MICE) approach. We will report the amount of missing data and apply appropriate methods to account for the missing data.

12. Planned Statistical Analyses

a. Baseline Demographics

The baseline characteristics of enrolled participants will be summarized in a table.

b. Efficacy Analyses Overview

Pre/post-survey outcome analyses will be conducted after all participants have been contacted and the survey is closed with missing responses marked as loss to follow-up.

- 1) **Descriptive Analyses:** Positive COVID test results will be summarized by counts. Vaccine status and COVID testing results will be presented as counts and percentages. Continuous variables will be summarized by mean, standard deviation (SD), and median (IQR). Secondary outcomes will be compared using Chi-squared tests.

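### The only PROMIS pre score is taken at enrolment, months before the materials are sent, so the pre/post change cannot be separated from unexposed time and season (and, for child scores, growth)

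*SAP*

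**What the plan says.** - **Design.** SAP 2 describes "a single-arm pre/post study". There is no concurrent control.
- **Measurement occasions.** SAP 7b lists PROMIS activity, sleep, stress, depression and anxiety for children and for parents, and states: "The outcome measures will be collected at pre-and post-assessment".
- **When the pre score is taken.** Under Protocol VI, a parent who enrols online will consent and then "complete a baseline survey (same enrollment and secondary outcomes survey from the RCT of the main study"; telephone enrolment covers the same questionnaires. Protocol I and SAP 3 date this stage: "Recruitment, enrollment, and baseline assessment are expected to last two months (September-November 2022". Neither document describes a later survey before mailing.
- **When the materials are sent.** SAP 3 (and Protocol I) says: "Enrolled participants will not receive the comic book and parent video series until after completion of the ROSSEY RCT Post 1 follow-up Survey". The date of Post 1 is not given. Protocol VI, under Risk Communication, ties mailing to the end of the RCT instead: "All intervention materials (i.e., children's comic books and parent videos) will be distributed after the final assessment of the larger ROSSEY RCT study is complete". It sets the timing as "within two weeks of completion of the ROSSEY RCT final assessment (December 2023".
- **When the post score is taken.** Protocol VI, under Follow-up Survey: "We will contact parents 6 weeks after the risk communication intervention distribution". The post assessment then stays open for 6 weeks. Protocol I and SAP 3 place follow-up in July-August 2023, 10 months after recruitment starts.
- **Analysis.** SAP 6 promises pre and post means, standard deviations and a p value. SAP 12b names chi-squared tests for the secondary outcomes. Neither section has a term for elapsed time, season or age.

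**The concern.** The secondary objectives in SAP 2 are causal. They ask whether providing the comic books and videos will raise activity, improve sleep and improve emotional regulation or mood. Answering them needs a pre score that describes families shortly before the materials arrive. Here the score is taken at enrolment, and the materials are then deliberately withheld for months to protect the RCT from contamination through siblings. Whatever happens to sleep, activity or mood in those months enters the pre/post change.

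The season also differs between the two scores, and the children, aged 3 to 5 at entry, grow older. Growth bears only on the child scores; elapsed time and season bear on the parents' scores too. A change of either sign could therefore appear without any effect of the materials, and a real benefit could be masked. Control of the false discovery rate (SAP 10) does not help, because this is bias and not multiplicity.

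**Working it through.** **1. The plan's own figure.** 1 September 2022 to 1 July 2023 is 10.0 months, so the follow-up date in Protocol I and SAP 3 agrees with itself. It does not agree with Protocol VI. Mailing on 1 December 2023 plus 6 weeks is 12 January 2024, which is 16.4 months after 1 September 2022.

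**2. Inputs.**
- Baseline: 1 September to 30 November 2022, the outer limits of the stated months. Recruitment itself is planned for about two months, so the true spread should be narrower.
- Response: 6 to 12 weeks after mailing (42 to 84 days), which is the 6-week rule plus the 6-week survey window.
- One month = 30.44 days.

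**3. Formula.** Unexposed share = (mailing − baseline) / (follow-up − baseline).

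**4. Schedule A: follow-up in July-August 2023, with mailing placed 6 to 12 weeks earlier.** This combines the dates in Protocol I and SAP 3 with the 6-week rule in Protocol VI.

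| Baseline to follow-up | Days | Response 6 weeks after mailing | Response 12 weeks after mailing |
|---|---|---|---|
| 30 Nov 2022 to 1 Jul 2023 | 213 (7.0 months) | 171/213 = 80% | 129/213 = 61% |
| 1 Sep 2022 to 31 Aug 2023 | 364 (12.0 months) | 322/364 = 88% | 280/364 = 77% |

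Between 61% and 88% of the interval is unexposed. Baseline to mailing is 129 to 322 days (4.2 to 10.6 months). The comparison is autumn with summer.

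**5. Schedule B: mailing from 1 December 2023 to 14 January 2024.** The later limit is the end of December plus the two weeks allowed.

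| Baseline to mailing | Days | Response 6 weeks after mailing | Response 12 weeks after mailing |
|---|---|---|---|
| 30 Nov 2022 to 1 Dec 2023 | 366 (12.0 months) | 366/408 = 90% | 366/450 = 81% |
| 1 Sep 2022 to 14 Jan 2024 | 500 (16.4 months) | 500/542 = 92% | 500/584 = 86% |

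The interval is 408 to 584 days (13.4 to 19.2 months), of which 81% to 92% is unexposed. Responses fall between 12 January and 7 April 2024, so autumn is compared mainly with winter.

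**6. What drift could do (illustration only).** The documents give no drift and no correlation between the two scores; both are assumed here. Take n = 50 (SAP 4), T-score SD 10 (SAP 7b), two-sided 0.05 and a paired comparison of means, which is not the chi-squared test named in SAP 12b. SD of change = 10 × √(2(1 − ρ)), and the drift is divided by SD/√50.

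| Assumed ρ | SD of change | p < 0.05 with 2-point drift | p < 0.05 with 3-point drift |
|---|---|---|---|
| 0.4 | 11.0 | 25% | 49% |
| 0.6 | 8.9 | 35% | 66% |
| 0.8 | 6.3 | 61% | 92% |

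All of these assume that the materials have no effect; the nominal rate is 5%.

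**The case against.** The single arm and the delay are both openly stated, and the delay has a sound reason. These are secondary outcomes of a small ancillary study without a power calculation, and any uncontrolled pre/post comparison carries drift. All of that stands, and it limits how much weight the point can bear. It does not explain why the baseline was left at enrolment once mailing had been deferred. That part is avoidable within a single arm.

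Four further objections also have force:
- **The Schedule A shares rest on an inference.** Protocol I and SAP 3 date neither Post 1 nor mailing. Without the 6-week rule from Protocol VI, an earlier Post 1 would allow a longer exposure.
- **Counting exposure as exactly 6 weeks would understate it.** The survey window extends it to as much as 12 weeks, so the exposed share reaches 39% on Schedule A and 19% on Schedule B. Most of the interval is still unexposed.
- **The documents give no recall period for the PROMIS items.** The argument therefore uses only the dates on which the surveys are taken.
- **The protocol is dated 1/03/24, after its own December 2023 mailing date.** On that schedule a survey before mailing may no longer be possible.

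A reader might infer that most of the observed change will be drift, season or growth. The documents do not support that. They give no size for any of these or for the effect of the materials; only the share of time is shown. A reader might also put the December 2023 mailing beside the July-August 2023 follow-up and conclude that nobody is exposed at follow-up. That is a contradiction in the dates to be resolved, not evidence of what was done.

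**Conclusion.** The point holds in a limited form. Even if the plan is followed exactly, the PROMIS change from enrolment to follow-up cannot be attributed to the materials, because it cannot be separated from unexposed elapsed time and season or, for child scores, from growth. The unexposed part is about 61% to 88% of a 7- to 12-month interval, or about 81% to 92% of a 13- to 19-month interval, depending on which schedule applies. The first range assumes that the 6-week rule applies to the July-August 2023 follow-up; the second assumes the December 2023 mailing. Both take responses at 6 to 12 weeks after mailing.

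The schedules are incompatible: follow-up in July-August 2023 would precede a mailing in December 2023. Until those passages are reconciled, no pre/post interval is defined. The causal secondary objectives cannot be answered as written. The change should be made, but it concerns secondary outcomes only.

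**What to change.** 1. Reconcile Protocol I and SAP 3 with Protocol VI on which RCT assessment releases the materials, when they are mailed and when follow-up takes place.
2. Repeat the existing REDCap secondary-outcomes survey after that RCT assessment closes and before mailing, in a protected slot. The two weeks in Protocol VI are an upper limit on mailing, not a reserved gap. Protocol VI still carries a placeholder for a baseline survey section, where this can be described.
3. In SAP 7b and 12b(3), define the pre-mailing score as the pre value. The pre-to-post interval becomes about 6 to 14 weeks: up to 2 weeks before mailing plus 6 to 12 weeks after it. Report the change from enrolment to pre-mailing beside it as unexposed drift.
4. Treat a missed pre-mailing survey as missing under SAP 11. Substituting the enrolment score would mix intervals of weeks with intervals of many months.
5. If mailing has already happened, restate the secondary objectives as description of change from enrolment to follow-up, without attributing it to the materials. RCT comparison students should not stand in as a control, because the documents do not show that they were surveyed at matching dates.

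The cost is one more survey contact for about 50 families, some staff telephone time and some non-response. The repeat survey reduces confounding by time, season and growth, but it does not replace a concurrent control. The fallback in item 5 costs only wording.

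### The secondary PROMIS outcomes are continuous T-scores measured before and after in the same people, but the only test the SAP names for them is chi-squared

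*SAP*

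**What the plan says.** SAP section 7b lists physical activity, sleep, stress, depression and anxiety, each for children and for parents, which makes ten secondary outcomes. It fixes their scale: "The final score is represented by the T-score, a standardized score with a mean of 50 and a standard deviation (SD) of 10". On timing it says: "The outcome measures will be collected at pre-and post-assessment". Section 2 gives the design as "a single-arm pre/post study", so the only comparison available is within person, over time.

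Section 6 sets out what will be reported: "For each of the continuous outcomes (including the primary outcome), the mean and standard deviation will be presented pre/post intervention and p value". Binary outcomes are treated separately there, with percentages and frequencies.

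The only statement on how the secondary outcomes will be tested closes the descriptive paragraph, section 12b(1): "Secondary outcomes will be compared using Chi-squared tests". Section 12b(3), headed for the secondary outcomes, lists the instruments again and gives no method. Neither document gives a cut-point or category for a T-score. The protocol contains no analysis section that would fill the gap.

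**The concern.** A Pearson chi-squared test works on counts in categories. To apply it to a T-score, the analyst must either cut the score at a value the SAP does not give, or treat each distinct score as its own category, which leaves most cells nearly empty with 50 people. Either way, the p value printed beside the pre and post means would not be a test of the difference between them.

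The standard test also assumes independent observations. Here each person contributes one score before and one after, so the two columns of the table are correlated.

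Three things follow:

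- Information is lost twice, through categorising and through ignoring the pairing. A real change in mental health, sleep or activity could easily be missed.
- An unstated cut-point can be chosen after the data are seen.
- The planned control of the false discovery rate (section 10) would be applied to p values that do not address the secondary objectives.

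**Working it through.** The SAP gives no effect size, power or pre/post correlation, so there is no figure of its own to reproduce. The calculation below only shows what the choice of test costs.

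**Inputs from the SAP**
- N = 50 (sections 4 and 5; section 2 and the protocol say no sample size is defined).
- SD = 10 (section 7b). This is the reference SD of the scale, not an estimate from this population.
- Alpha = 0.05 (section 12b(2), stated for the primary analysis only).

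**Assumptions not in the documents**
- 50 complete pairs, normal scores and a pre-intervention mean of 50.
- A true change of 4 points.
- Pre/post correlation r of 0.3, 0.5 or 0.7.
- Cuts at 50, 55 or 60.
- Two-sided testing with no multiplicity adjustment.

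**Paired t-test.** SD of change = 10 × √(2(1 − r)). Noncentrality = 4 / (SD of change / √50). Power comes from the noncentral t with 49 df (critical value 2.01).

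| r | SD of change | Noncentrality | Power |
|---|---|---|---|
| 0.3 | 11.83 | 2.39 | 65% |
| 0.5 | 10.00 | 2.83 | 79% |
| 0.7 | 7.75 | 3.65 | 95% |

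The smallest mean change detectable with 80% power is (1.96 + 0.84) × SD of change / √50, which is about 4.7, 4.0 and 3.1 points respectively.

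**Chi-squared on cut scores.** Correlated normal scores were simulated (40,000 trials per scenario), cut, and compared by an uncorrected Pearson test that treats pre and post as independent groups. The direction of change matters once the cut is away from 50. A 4-point fall takes the share at or above 60 from 15.9% to 8.1%, and a 4-point rise takes it to 27.4%. Power:

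| r | 4-point fall: cut 50 / 55 / 60 | 4-point rise: cut 50 / 55 / 60 |
|---|---|---|
| 0.3 | 35% / 29% / 21% | 34% / 33% / 27% |
| 0.5 | 33% / 27% / 20% | 33% / 32% / 26% |
| 0.7 | 31% / 25% / 17% | 31% / 30% / 23% |

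**Under no change** (cut at 50), the chi-squared test rejects in about 3.4%, 2% and 0.7% of trials at r = 0.3, 0.5 and 0.7, instead of 5%. Ignoring the pairing makes it too conservative, and more so as the correlation rises. This is why chi-squared power falls with r while paired-t power climbs.

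**The case against.** The strongest reply is that this is a drafting slip. The sentence sits under descriptive analyses, section 6 already separates continuous from binary outcomes, and the authors may never have meant to categorise T-scores. That is plausible. But the sentence is the only test named for these outcomes. Without it the SAP has no test for them at all, while section 6 still promises a p value. The text needs correcting on either reading.

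A second reply is that a chi-squared statistic can come from a Wald or likelihood-ratio test in a mixed model, which would be valid. True, but no model is specified.

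Third, the SAP never says in so many words that it will test a change in means. That is an inference from section 6 and from the directional objectives in section 2, though no other reading fits the promised table of means.

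Fourth, the power figures are soft, and this stands. With 40 complete pairs and r = 0.5, paired-t power for a 4-point change falls to 69%, and with 30 pairs to 56%. A 2-point change with 50 pairs gives only 28%. Control of the false discovery rate would lower all of these. A paired test does not make this small study well powered in general.

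Finally, these are secondary outcomes of an uncontrolled ancillary study with no power target, which limits how serious the point is.

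**Conclusion.** The concern holds. Followed literally, the SAP attaches to each pair of T-score means a p value that does not test their difference and that treats repeated measurements as independent. That conclusion follows from the text alone.

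In the illustrated scenario, the paired t-test has 65% to 95% power over correlations of 0.3 to 0.7, and the chi-squared test has 17% to 35% across both directions of change and the three cuts. A real change of that size would more often than not be missed. The size of the gap depends on the assumed change, correlation, baseline mean, cuts and complete follow-up. The point should be corrected, but because it concerns secondary outcomes it does not threaten the primary analysis.

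**What to change.** Delete the chi-squared sentence from SAP section 12b(1). In 12b(3), state that each PROMIS T-score will be analysed as a within-person change, by one of these:

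- a paired t-test; or
- a linear mixed model with time as a fixed effect and participant as a random effect, which also uses people who answered only one survey.

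Report the mean change with a 95% confidence interval beside the pre and post means and SDs. A Wilcoxon signed-rank test is a reasonable but optional sensitivity analysis. State that the false discovery rate control in section 10 covers these p values; the imputation sensitivity analysis in section 11 can stay as planned.

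The cost is one or two sentences and no new data. The SAP is dated June 30, 2022 and the protocol was updated on 1/03/24, so outcome data may already have been seen. The change should therefore be dated and justified, and declared post hoc if it was made after the data were seen.

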- 2) **Primary Objectives:** The primary analysis of vaccine uptake and COVID testing will be conducted using a chi-squared test using $\alpha = 0.05$ and report pre/post changes over time.
- 3) **Secondary outcomes:** The secondary outcomes for the trial include measures from the PROMIS – Pediatric and Parent Proxy Instruments. The PROMIS instruments used are children's PA, sleep, stress, depression, and anxiety and parents' PA, sleep, stress, depression, and anxiety.

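### Vaccine uptake: the planned chi-squared test, as written, does not account for pairing, and no rule derives post-survey status from the item on doses since enrollment

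*SAP*

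**What the plan says.** SAP 2 describes a single-arm pre/post design, and its primary objective concerns testing and vaccine uptake in children. On the analysis, SAP 12b(2) states: "The primary analysis of vaccine uptake and COVID testing will be conducted using a chi-squared test", at alpha 0.05, with changes from pre to post reported. No form of the test is specified. SAP 6 adds that for binary outcomes the frequency and percentage (its example is "percentage vaccinated) will be presented pre/post and p value") are shown.

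SAP 7a defines the outcome through two different questions. At baseline: "Parents are asked at enrollment to report their vaccination status and their child's vaccination status". At the post survey the parent is asked "if they or their child have received any COVID-19 vaccine or booster since enrollment". The only coding statement is: "Vaccination status will be a binary, yes/no variable". The Protocol (VI, Follow-up Survey) describes the follow-up questions as covering "updates to their contact and demographic information, child's COVID-19 vaccination status".

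On who is analysed, SAP 7a says: "All children and parent data will be included in the intention-to-treat analysis". SAP 12b runs the analysis once "the survey is closed with missing responses marked as loss to follow-up". SAP 10 promises FDR control without naming the family or the level. SAP 11 makes multiple imputation by chained equations (MICE) a sensitivity analysis.

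**The concern.** There are two linked gaps.

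**Test.** Each child contributes a pre and a post value, and these are strongly correlated because a vaccinated child stays vaccinated. A Pearson test on the time-by-status table ignores that correlation and uses too large a standard error for the change. It is conservative, and may report no change when a clear share of children was newly vaccinated.

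**Outcome.** The enrollment item measures status (a prevalence). The post item measures new doses (an incidence) and, as described, joins parent and child. Nothing says how the two become one yes/no post status, or how a booster in an already vaccinated child counts. If the post answer alone were used, every child vaccinated at enrollment without a further dose would count as no. A paired test does not repair that.

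At stake are the p value, and possibly the direction, of a co-primary result.

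**Working it through.** **Inputs.** The documents give no baseline rate, expected uptake or dropout, and no power figure to reproduce. SAP 4 and 5 give 50 participants; SAP 2 and Protocol IV say that no sample size is defined. Assumed here: 50 children with both reports, 20 vaccinated at enrollment (40%), 6 first vaccinations by the post survey, two-sided tests, and Pearson without continuity correction.

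**1. Cumulative status (yes stays yes): 20/50 to 26/50.**
- Pearson, two independent groups of 50: 100 × (20×24 − 30×26)² / (50×50×46×54) = 1.449, p=0.229.
- Exact McNemar, 6 changes from no to yes and 0 from yes to no: 2 × 0.5⁶ = 0.031.
- Standard error of the 12-point change, unpaired: √(0.40×0.60/50 + 0.52×0.48/50) = 0.099. Paired: √(6 − 6²/50)/50 = 0.046.
- Newly vaccinated among all children: 6/50 = 12% (exact 95% CI 4.5% to 24.3%). Among those unvaccinated at enrollment: 6/30 = 20% (exact 95% CI 7.7% to 38.6%).

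**2. Dependence on the base rate.** The fewest new vaccinations out of 50 children that give p<0.05:

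| Vaccinated at enrollment | Pearson | Exact McNemar |
|---|---|---|
| 5 | 8 | 6 |
| 10 | 9 | 6 |
| 15 to 25 | 10 | 6 |

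From 20/50, 9 new vaccinations give Pearson p=0.072 and 10 give p=0.046.

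**3. FDR control.** If the family were the two co-primaries (an assumption) and the testing outcome were not significant, Benjamini-Hochberg would require p≤0.05/2 = 0.025. Six new vaccinations (0.031) would then not suffice; seven would (2 × 0.5⁷ = 0.016).

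**4. Post item used alone.** Take the same children, with b of the 20 already vaccinated having a booster. The post count is 6 + b, which is below 20 whenever b<14.

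| Boosters b | Pre to post | Pearson p | Exact McNemar p |
|---|---|---|---|
| 0 | 20 to 6 | 0.0014 | 0.0094 |
| 5 | 20 to 11 | 0.052 | 0.078 |
| 10 | 20 to 16 | 0.40 | 0.45 |

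In every row cumulative coverage rose to 26/50. The apparent fall comes from the coding, and both tests show it.

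**5. Which children have a known post status.** Under cumulative coding, a child vaccinated at enrollment is a yes at post whether or not the family answers again. Dropping such children inflates the all-child figure: if 10 of the 20 had no post survey and were removed, 6/50 = 12% would become 6/40 = 15%. The at-risk figure, 6/30, would not change.

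**The case against.** McNemar's statistic is itself referred to a chi-squared distribution, so the SAP's wording does not strictly exclude a paired test. That stands: a reader might infer that the plan commits to an unpaired test, and it does not say so. But no paired form is named anywhere, and SAP 12b(1) uses the same generic term for comparing the secondary outcomes, so the Pearson reading is the natural one.

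A reader might also infer that the plan will report a fall in vaccination. The documents do not support that. The variable is called vaccination status, SAP 6 speaks of a percentage vaccinated, and the Protocol describes updates to the child's status, all of which point to cumulative coding. The survey items are not in the documents, and the phrase joining parent and child may summarise separate questions. The sign change is a possible result of an unwritten rule, not of a planned coding.

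A third tempting inference is that pairing recovers a large amount of power. For an assumed rise from 40% to 55% in 50 children with no reversals, Pearson rejects about 21% of the time and exact McNemar about 78% (7% and 64% if p≤0.025 is needed). Under cumulative coding, however, McNemar's null is that nobody was newly vaccinated, so the 78% is only the chance of six or more new vaccinations. It is not power for an intervention effect.

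Finally, the harm under cumulative coding is bounded. A conservative test adds no false positives, and the pre and post percentages would be reported anyway. That is a fair reason to let the estimate and its interval carry the result, but not to keep a p value built on the wrong standard error.

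**Conclusion.** The point holds for vaccine uptake. As written, the test does not account for pairing, and the rule for post status is missing. In the illustration, ignoring the pairing roughly doubles the standard error of the change (9.9 against 4.6 points) and moves p from 0.031 to 0.23, before FDR control. The sizes rest on assumed rates and 50 complete pairs. The direction does not depend on the base rate: across 5 to 25 of 50 vaccinated at enrollment, Pearson needs 8 to 10 new vaccinations and exact McNemar needs 6.

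The missing derivation rule is the more consequential gap, because the choice of coding can change the sign and no choice of test cures it. The more probable coding is cumulative, and the SAP should say so. Neither correction turns a single-arm rise in a status that can only increase into evidence that the materials worked.

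**What to change.** 1. **SAP 7a, derivation.** Define the child's post status as yes if the child was vaccinated at enrollment or if any dose is reported for the child since. Report boosters in already vaccinated children separately. First check that the survey recorded child and parent answers, and first doses and boosters, separately. If it did not, say so and report the combined item descriptively, without a pre/post p value.
2. **SAP 12b(2), analysis.** Replace the chi-squared test for vaccine uptake with a paired analysis. Lead with the number and proportion newly vaccinated among children unvaccinated at enrollment, and with the change in percentage vaccinated among all children, each with a 95% CI. Give an exact McNemar p value as secondary, within the FDR control of SAP 10. Analyse parents separately in the same way.
3. **Missing post surveys.** Reconcile the intention-to-treat sentence in SAP 7a with this. Children vaccinated at enrollment stay yes at post even without a post survey. Only children unvaccinated at enrollment who lack a post survey are missing; report their number and include them through the planned MICE sensitivity analysis. Compute the pre and post percentages on the same children.
4. **Interpretation.** State that cumulative vaccination can only rise, so the result describes change over time and is not evidence of an intervention effect.

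The cost is a few sentences in SAP 7a and 12b(2), and no new data if the items were recorded separately. The downside is that children unvaccinated at enrollment without a post survey enter only through the sensitivity analysis.
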